## 3.2 Study Population

### 3.2.1 Eligibility Criteria

Eligible subjects for the cognitive interviews must:

*Child inclusion criteria*

- Be 5 to 11 years of age
- Have asthma
- Currently use a maintenance inhaler to treat their asthma
- Be willing and able to provide assent
- Be willing and able to participate in a 45-minute interview in English

#### *Caregiver inclusion criteria*

- Be 18 + years of age
- Be a caregiver (parent or legal guardian) of a child with asthma that meets the criteria above
- Be willing and able to provide signed and dated informed consent and parental permission in English
- Be willing and able to participate in a 45-minute interview

### **3.2.2 Sampling**

The patient population will consist of a convenience sample of child and caregiver dyads. Participants will be screened and recruited for the study based on the above listed inclusion criteria which were developed with the aim of recruiting a population similar to that included in the planned clinical trial.

### **3.3 Data Source / Data Collection**

All data will be provided by interview participants either during recruitment or during the interview. The qualitative research facilities will enter demographic and asthma-specific data provided by participants into a Microsoft Excel spreadsheet and provide it to RTI-HS. The qualitative data from the interviews will be systematically collected by RTI-HS via field notes and audio recordings. Following the conclusion of the interviews, all audio files will be transcribed and prepared for analysis.

#### **3.3.1 Endpoints**

##### **3.3.1.1 Primary Endpoint**

The evaluation of items to assess ease of inhaler use for implementation in clinical trials with pediatric patients aged 5 to 11 years and their caregivers.

##### **3.3.1.2 Secondary Endpoint**

The determination of the number of participants aged 5 to 11 years able to produce an audible sound using the ELLIPTA whistle.

### **3.4 Sample Size / Power Calculations**

Target population of 16 of child/caregiver dyads consisting of 1 child (aged 5 to 11 years) with asthma currently using a maintenance inhaler and his or her caregiver (for a total sample of 32 participants). The interviews will be conducted in two iterative sets (approximately 8 dyads or 16 participants per set) to allow for refinement of the items between sets.

Formal sample size calculations based on hypothesis testing were not performed due to the qualitative nature of this study. However, conducting two sets of interviews with a targeted total of 32 individuals is

expected to provide an adequate sample for systematic qualitative analysis and assessment of the research objective.

Specifically, it is anticipated that the comprehension and appropriateness of the instructions and items will be fully demonstrated across the evaluated age range by the completion of the second set of interviews. However, if participants provide feedback or the interviewers observe that the instructions or items are not clear or that the measure does not fully assess key ease of use inhaler attributes, an increased sample size would be recommended (e.g., revision of the items and the conduct of additional set[s] of interviews).

### **3.5 Hypotheses**

Not applicable

## **4 DATA ANALYSIS CONSIDERATIONS**

RTI-HS will perform descriptive analyses to summarize the demographic and clinical data provided by participants at screening and qualitative analysis of interview data. The descriptive analyses will include the computation of frequencies and percentages for categorical variables (e.g., gender, education level) and the computation of means, standard deviations, and ranges for continuous variables (e.g., current age, age at diagnosis). The number of participants aged 5 to 11 years who are able to produce an audible sound using the ELLIPTA whistle will also be reported, as will the number of attempts required (up to 3 attempts per participant).

Analysis will follow standard qualitative data-collection and analysis methods that include two main guiding principles: researcher neutrality and systematic process. Data will be systematically collected via field notes and audio recordings.

Following the conclusion of the patient interviews, all audio files will be transcribed and prepared for analysis.

Analysis of the resulting data (captured in both field notes and transcripts) will ensure that an accurate reflection of the combined results (across interview sets) has been captured.

The analysis goal of the first set of interviews is to evaluate the proposed mode of administration by age group and identify any initial problems with item wording or response options. The analysis goal of the second and final set of interviews is to test the adequacy of modifications based on the first set of interviews, inform any further revisions required to optimize the items, and gather additional qualitative data about the final item set before implementation in the clinical trial. Each interview also offers an opportunity to identify any additional concepts patients and/or their caregivers think should be addressed regarding ease of use (if any) in order to contribute to the content validity of the final instrument.

A final report will summarize the entire questionnaire development process, including analysis methods and results. The summary report will describe the implications of the cognitive debriefing interviews,

including rationale for item development, modification(s), and mode of administration by age. In addition, the report will include representative quotes from participants.

## **5 LIMITATIONS**

One limitation of this study design rests in its qualitative nature. While data obtained from participants are considered reliable, their external validity cannot be confirmed as generalizable to the entire population of individuals with asthma who may participate in a clinical study.

Response bias is another potential limitation associated with the proposed design in that individuals willing to participate in a clinical trial of a new treatment may be different than those willing to participate in a qualitative study. For instance, those who agree to participate in a clinical trial may experience a greater severity of asthma. Both of these limitations have been addressed by designing the selection criteria for the cognitive debriefing interviews to be similar to the clinical trial criteria.

## **6 STUDY CONDUCT, MANAGEMENT & ETHICS**

### **6.1 Ethics Committee/IRB Approval**

RTI International's (RTI's) institutional review board (IRB) will review and approve the study protocol, screening materials, all data-collection materials, and the informed consent documents.

RTI, of which RTI-HS is a part, holds a Federal-Wide Assurance (FWA #PPD effective until June 16, 2020) from the US Department of Health and Human Services (DHHS) Office for Human Research Protections (OHRP) that allows for the review and approval of human subjects protocols through the IRB committees. These committees are also registered with OHRP for research regulated by both the US DHHS and the Food and Drug Administration (FDA) (registration expires February 2, 2020). The RTI FWA requires IRB review for all studies conducted by RTI that involve human subjects, regardless of the funding source. Depending on the level of risk and nature of the research, a study may be ruled as exempt from IRB review by an IRB chair or designated IRB member. Studies that are not exempt must be approved either by an IRB chair or designated IRB member (if the study qualifies for expedited review) or by a full IRB committee.

RTI currently has three IRB committees available to review research protocols. Each committee meets monthly. One of the IRBs is constituted with appropriate medical expertise among its members to review biomedical clinical trials. These IRBs have been audited by the FDA and are fully compliant with applicable regulatory requirements. The committees review research studies to ensure adherence to appropriate regulations that govern human subjects research, including the Code of Federal Regulations 45, CFR 46, and 21 CFR 50 and 56, and with all applicable provisions of the International Conference on Harmonisation. All studies involving human subjects undergo an annual IRB review.

RTI-HS will obtain prospective approval of the study protocol, protocol amendments, informed consent forms, and any other relevant documents from one of the three RTI IRB committees.

Compliance with GSK and regulatory standards provides assurance that the rights, safety, and well-being of patients participating in non-interventional studies are protected (consistent with the principles that have their origin in the Declaration of Helsinki) and that the study data are credible and responsibly reported.

This study was designed and shall be implemented and reported in accordance with the Guidelines for Good Pharmacoepidemiology Practices of the International Society for Pharmacoepidemiology (2007), the STROBE (Strengthening the Reporting of Observational Studies in Epidemiology) guidelines (von Elm et al., 2008), and with the ethical principles laid out in the Declaration of Helsinki.

## **6.2 Informed Consent**

Prior to each interview, RTI-HS staff will conduct the informed consent discussion, comprised of the informed consent discussion with parents/guardians, and the parental consent and child assent discussion with the parents/guardians and the child/interview participant.

This discussion will include (but will not be limited to) an overview of the study procedures, the voluntary and confidential nature of the research, and audio recording details. Children and parents/guardians will be encouraged to ask any questions about the study at this time. If the parent/guardian agrees to participate in the interview, he/she will sign and date the parental informed consent form. If the child agrees to participate in the interview, the child will be asked to acknowledge assent (if appropriate) on the child assent form. Signed consent, permission, and assent forms will be maintained by RTI-HS in a controlled documents room accessible only to the RTI-HS project team and separate from other study documentation. Each parent and participant will be given an unsigned copy of both the parental consent and assent forms.

## **6.3 Data Protection**

The qualitative research facilities will enter demographic and asthma-specific data provided by participants into a Microsoft Excel spreadsheet provide it to RTI-HS.

The qualitative data from the interviews will be systematically collected by RTI HS via field notes and audio recordings. All information provided during the interview will be kept highly confidential. Patient interviews will only use first names for participants. These first names will not be included in the study report. While the interviews will be audio recorded and transcripts will be made from the audio recording of the interviews, participants' names will never be associated with the responses given. Any names (even first names) mentioned during the course of the discussions will be omitted from the transcripts. Upon completion of the transcripts and final written report, all audio recordings will be destroyed.

All signed and dated informed consent (the only form with identifying information will be maintained at RTI-HS in a secure location (a controlled documents room) separate from other study documentation to further ensure participant confidentiality.

If the results of this study are presented at scientific meetings or published in scientific journals, no information will be included that could identify you or your answers personally. Publications will comply with internal GSK standards and the International Committee of Medical Journal Editors guidelines.

#### **6.4 Personally Identifiable Information (PII)**

All patient information collected during the patient interviews will be de-identified as described above. No patient information will be associated or linked to any particular participant.

#### **6.5 Adverse Event (AE), Pregnancy Exposure, and Incident Reporting**

No solicited safety data capture is required for prospective studies using primary data collection without a GSK drug of interest. However, if during the course of the study participation an adverse event suspected to be associated with the use of a GSK product is identified in a patient, it must be reported to the local health authority in accordance with national regulatory requirements for individual case safety reporting, and a spontaneous report must be sent to GSK. Adverse reactions identified for non-GSK products should be reported to the local health authority in accordance with national regulatory requirements for individual case safety reporting or the marketing authorization holder.

## **APPENDIX A: ADULT EASE OF USE ITEMS**

## **ELLIPTA Inhaler Ease of Use Questionnaire**

Paper copies of the Ease of Use questions will be used by the administrator (Investigator or designee) to record subjects' answers to the questions. The site will enter the answers into the electronic case report form (eCRF).

**INSTRUCTIONS:** The administrator (Investigator or designee) will complete the following questions related to the ELLIPTA inhalers used during this study. **Check only one** response for the question asked.

Survey questions VERSION "A" **OR** "B" to be completed at visit 2 per randomization at visit 2.

### **ELLIPTA Inhaler Questionnaire (VERSION A)**

Instructions: Please complete the following questions related to the ELLIPTA inhaler that you used during this study. Choose only one response for each question.

1. How easy or difficult is it to use the ELLIPTA inhaler?  
 Very easy  
 Easy  
 Difficult  
 Very difficult
  
2. How easy or difficult is it to tell how many doses are left in the ELLIPTA inhaler?  
 Very easy  
 Easy  
 Difficult  
 Very difficult
  
3. If your current daily inhaled COPD medication was available in the ELLIPTA inhaler, how likely or unlikely would you be to request the medication in the ELLIPTA inhaler from your doctor?  
 Very likely  
 Likely  
 Unlikely  
 Very unlikely

## **APPENDIX B: PEDIATRIC AND CAREGIVER EASE OF USE ITEMS**

**Interviewer-administered version (recommended for ages 5-7 and any participants that appear to have difficulty reading the self-administered version for ages 8-11). To be administered by trained clinic-staff (not the parent or caregiver).**

Instructions: "I am going to ask you some questions about using this inhaler [interviewer has demonstrator ELLIPTA]. The name of the inhaler is ELLIPTA. I will read the question and answers to you. Then I will ask you to choose the answer that matches what you thought about using the ELLIPTA at home. Do you have any questions for me?"

[Pause and answer any questions from participant. After answering any questions, read the first question and the responses as written below. Repeat the question and responses as needed for the participant. Once the participant has selected a response, read the second question and responses. If the child needs help in understanding the questions or responses, you can explain or define individual words but please take care not to influence his or her answer].

1a. How easy is it to use the ELLIPTA inhaler?

- Very easy
- Easy
- Hard
- Very hard

Or

1b. Is it easy to use the ELLIPTA inhaler?

- Yes
- No

Or

1c. How easy is it to use the ELLIPTA inhaler?

Very easy

Easy

Hard

Very hard

2a. How easy is it to tell how many puffs are left in the ELLIPTA inhaler?

- Very easy
- Easy
- Hard
- Very hard

Or

2b. Is it easy to tell how many puffs are left in the ELLIPTA inhaler?

- Yes
- No

Or

2c. How easy is it to tell how many puffs are left in the ELLIPTA inhaler?

Very easy

Easy

Hard

Very hard

**Self-completed version (recommended for ages 8-11). For any participants that have difficulty completing self-administered version, the interview-administered version for ages 5-7 can be used.**

Proposed verbal instructions to be read by trained clinic staff: "I am going to give you a paper with two questions about the inhaler you used during the study [interviewer has demonstrator ELLIPTA]. The name of the inhaler is ELLIPTA. Read the questions and choose the answer that best matches what you thought about using the ELLIPTA at home. Do you have any questions?" [Pause and answer any questions from participant. If participant needs help in understanding the questions or responses, you can explain or define individual words but please take care not to influence his or her answer].

Please choose one answer.

1a. How easy is it to use the ELLIPTA inhaler?

- Very easy
- Easy
- Hard
- Very hard

[figure not shown]
Or

1b. Is it easy to use the ELLIPTA inhaler?

[figure not shown]
- Yes
- No

Or

1c. How easy is it to use the ELLIPTA inhaler?

Very easy

Easy

Hard

Very hard

2a. How easy is it to tell how many puffs are left in the ELLIPTA inhaler?

- Very easy
- Easy
- Hard
- Very hard

Or

P  
P  
D

2b. Is it easy to tell how many puffs are left in the ELLIPTA inhaler?

[figure not shown]
- Yes
- No

Or

2c. How easy is it to tell how many puffs are left in the ELLIPTA inhaler?

Very easy

Easy

Hard

Very hard

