### **II. Discussion with Child: Warm-up (Same questions for all children)**

- Can you tell me about the inhaler that you use every day? Not the inhaler that might be called a "rescue" inhaler (for when you are having trouble breathing), but the one that you use all the time.
- What do you call this inhaler?
- What do you think about using [child's name for inhaler]? Is it hard to use? Why? Do you like to use it? Why (or why not)?
- Do you remember who taught you how to use [child's name for inhaler]? Was it hard to learn how to use it?
- Does anyone help you when you use it?
- How do you remember to use it every [night, morning or night and morning]?
- Do you know when the [child's name for inhaler] is almost out of medicine? How?

- Can you tell me how you take your medicine? Can you pretend you have your [child's name for inhaler] with you now and show me how you use it? How do you get the inhaler ready? After it is ready, what do you do to use it? What else do you have to do when you use your inhaler?
- Thank you for telling me about your [child's name for inhaler]. Now I want to ask you some questions about using an inhaler. When you are answering the questions, I want you to think about the inhaler that you just told me about we just talked about [Note: for the purposes of cognitive debriefing, replace ELLIPTA with the child's name of his/her maintenance inhaler, do this verbally for the children in the 5-7 age range, for the children that are 8-11 can update "ELLIPTA" on the questionnaire to the name that the child calls their inhaler (if just "inhaler" can put one line through ELLIPTA)].

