#### Debrief (Children 5-7):

*Instructions: I will read the question and answers to you. Then I will ask you to choose the answer that matches what you thought about using the [child's name for inhaler] at home. Do you have any questions for me?"*

1a. How easy is it to use the [ELLIPTA] inhaler?

- Very easy
- Easy
- Hard
- Very hard

[Interviewer notes the response selected by the child].

- Could you please tell me what it is about [child's name for inhaler] that makes you say it's [child's answer] to use? What did you have to think about to answer?
- Was it hard to understand my question? Why? Was it hard to choose an answer? Why?
- What would it be like if it was [opposite of what child chose – hard or easy]?
- Is easy and very easy the same for you or are they different? What things are easy for you? What things are very easy for you?
- Is hard and very hard the same for you or are they different? What things are hard for you? What things are very hard for you?

Thank you, now I have another question to ask you.

1b. Is it easy to use the [ELLIPTA] inhaler?

- Yes
- No

- What makes you answer [child's response] to this question? What did you have to think about?
- Is this question the same or different than the one we just talked about?
- Was this question easier or harder for you to answer? Why?

Thank you, now I am going to ask another question, but this time I have a different way for you to tell me your answer [interviewer provides child with sheet that has the item and responses, interviewer reads the question and the response under each face, when pointing to the face and asks the child to circle the face that matches their answer].

1c. How easy is it to use the [ELLIPTA] inhaler?

Very easy

Easy

Hard

Very hard

- Do you think the faces make it easier to answer the question? Why?
- [Only ask if a different response from 1a was chosen] You circled [child's response]. Why did you choose that answer?
- If you had to tell me about [select a face], what words would you use? What feeling does the face make you think of? Why?
- Which of the three questions that I asked you was the easiest to answer? Why?

Thank you, now we have three more questions for you before we talk to your [mom, dad, other caregiver].

2a. How easy is it to tell how many puffs are left in the [ELLIPTA] inhaler?

- Very easy
- Easy
- Hard
- Very hard

[Interviewer notes the response selected by the child].

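### Both yes/no child items score 'Yes' as favourable, and item 2 (puffs left) has no reversed question to check for habitual yes-saying before a format is recommended by age

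*Combined protocol and SAP*

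**What the plan says.** Appendix B gives three candidate formats for each child item: four options in words (1a, 2a), yes/no (1b, 2b) and four options with faces (1c, 2c). The yes/no forms are "1b. Is it easy to use the ELLIPTA inhaler" and "2b. Is it easy to tell how many puffs are left in the ELLIPTA inhaler". In the interviewer-administered and the self-completed versions alike, 'Yes' means easy.

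The Appendix C warm-up, which is headed as common to all children, asks about the child's own maintenance inhaler: "Is it hard to use? Why". It also asks "Do you know when the [child's name for inhaler] is almost out of medicine? How". The debrief then substitutes that same inhaler for ELLIPTA in the items.

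In both age modules the yes/no item is followed by three probes. The first asks for the reasoning behind the answer ("What makes you answer [child's response] to this question? What did you have to think about"), the second asks the child to compare the item with its predecessor, and the third is "Was this question easier or harder for you to answer? Why". After 1a the child also meets a probe beginning "What would it be like if it was [opposite of what child chose", and a similar one follows 2a. A probe for answers that differ appears only with the faces items. At 1c it compares with 1a; at 2c it again refers to 1a.

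Section 4 says that the report will give the rationale for modifications and for mode of administration by age. It does not say that 1b or 2b will be compared with any other answer.

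**The concern.** A child, particularly one aged 5 to 7 to whom an adult is reading the question, may say yes out of politeness or habit. On a yes/no item keyed in one direction, that answer looks the same as a true 'easy'. A question with the opposite key separates the two, because a habitual yes-sayer then contradicts himself or herself. Item 1 has such a question in the warm-up; item 2 does not. A child who says yes throughout is consistent on the warm-up question about running out of medicine and on 2b.

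The guide asks which version was easiest to answer. The shortest format could do well on that question whether or not its answers are valid. If yes/no were carried into the trial for younger children, yes-saying would raise the share recorded as finding it easy to tell what is left.

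**Working it through.** **The plan's own figures.** Section 3.4: 2 sets × 8 dyads = 16 dyads; 16 × 2 = 32 participants. Both reproduce. There is no hypothesis test, and no stated figure depends on how the items are keyed.

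**The checks, side by side (Appendix C).**

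| Check | Item 1 | Item 2 |
|---|---|---|
| Four-option answer given first | 1a | 2a |
| Child describes the opposite state | after 1a | after 2a |
| Child explains the yes/no answer | after 1b | after 2b |
| Warm-up question on the topic | reversed | same direction as 2b |
| Any reversed question to the child | yes | none |
| Written probe for differing answers | 1c against 1a | at 2c, but naming 1a |
| Probe if a and b disagree | none | none |
| Caregiver view | whether easy or hard for the child | who keeps track of remaining medicine |

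**Possible inflation (assumed rates).** Let p be the true share answering easy and a the share who always say yes, independent of true ease. Observed yes = p + (1 − p)a, so inflation = (1 − p)a.

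| p | a = 0.10 | a = 0.20 | a = 0.30 |
|---|---|---|---|
| 0.5 | 5 points | 10 points | 15 points |
| 0.7 | 3 points | 6 points | 9 points |
| 0.9 | 1 point | 2 points | 3 points |

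**Chance of seeing at least one contradiction on item 2 (assumed rates).** Let h be the share of four-option answers on the hard side. Assume that yes-sayers answer 2a truthfully and say yes to both yes/no forms.

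- 2a/2b pair alone: 1 − (1 − a·h)^n. With a = 0.20 and h = 0.15, this is 1 − 0.97^8 = 0.216 for n = 8 and 1 − 0.97^16 = 0.386 for n = 16.
- One reversed question: 1 − (1 − a)^n. With a = 0.20, this is 1 − 0.80^8 = 0.832 and 1 − 0.80^16 = 0.972.
- With h = 0.30, the pair gives 1 − 0.94^8 = 0.390 and 1 − 0.94^16 = 0.628.

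| n | Pair, a 0.1 to 0.3 and h 0.1 to 0.5 | Reversed question, a 0.1 to 0.3 |
|---|---|---|
| 4 | 4% to 48% | 34% to 76% |
| 8 | 8% to 73% | 57% to 94% |
| 16 | 15% to 93% | 82% to 99.7% |

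The row for n = 4 is there because the documents do not say how many children will be aged 5 to 7.

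With h = 1 − p, inflation and detection by the pair move together. At h = 0.15 and a = 0.20 the inflation is 0.15 × 0.20 = 3 points; at h = 0.30 it is 6 points, and the pair detects more. The reversed question adds most where the pair is weakest, which is also where the inflation is smaller.

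**Item 1.** If the warm-up question is asked of every child and compared with 1b, the reversed-question formula already applies: 83% for n = 8 and 97% for n = 16 at a = 0.20. A second reversed question would add nothing to that.

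**The case against.** The strongest reply is that cognitive debriefing already guards against this. The child must give a reason for the yes/no answer, compare it with the previous question and, after 2a, describe the opposite state. After 1a and 2a the child is also asked whether the question was hard to understand and whether it was hard to choose an answer, where a reflex yes is unfavourable and has to be explained. Interviews are recorded with notes on nonverbal cues, the caregiver gives an outside view, and there are two rounds, with further sets possible under Section 3.4. Yes/no is one of three formats under test, and nothing in the plan favours it.

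Most of this stands. A reader might infer that no reversed question is asked at all, or that the debrief cannot separate understanding from yes-saying. The warm-up contradicts the first inference for item 1, and the open probes contradict the second for both items. Nor is this the only chance to notice the problem.

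The reply leaves a gap for item 2. None of these checks reverses 2b itself, and a disagreement between 2a and 2b prompts no written question. For item 1, the reversed question is one of several prompts in a single bullet, and the guide's opening note says that it need not be followed verbatim. Against that, the warm-up heading says that all children get the same questions. Even if it is always asked, nothing directs anyone to compare the answer with 1b.

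**Conclusion.** The point holds as a limited design gap. Items 1b and 2b are keyed in one direction. Item 1 has a reversed question that the plan does not use in analysis; item 2 has none, and the discordance probe at 2c points to the wrong item. Yes-saying on 2b is therefore checked only in part.

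The size rests wholly on assumed rates of yes-saying and true ease. Inflation runs from 1 to 15 points over the ranges shown. The contrast of 22% with 83% (n = 8) concerns item 2, compares a reversed question with the 2a/2b pair alone, and gives no credit to the open probes, so it overstates the net gain. A reader might carry the same contrast over to item 1; it does not apply there where the warm-up question is asked and compared. The documents also do not show that the yes/no format will be chosen, so any bias in the later trial is conditional on that choice.

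**What to change.** 1. In both age modules of Appendix C, after the child says which version of item 2 was easiest, add one spoken yes/no check: the Appendix B wording of 2b with 'hard' in place of 'easy'. In this position it cannot affect the earlier item 2 answers.
2. Ask the existing reversed warm-up question for item 1 of every child, and record the answer.
3. Add a probe for any contradiction between 1b or 2b and the four-option or reversed answer to the same item, and correct the cross-reference at 2c to 2a in both modules.
4. In Section 4, state that these contradictions will be tabulated per child by age group, with the child's explanation, as evidence for choosing the format.

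There should be no automatic exclusion rule. With up to 16 children, one unexplained double 'Yes' is too little to rule out a format for a whole age group.

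The cost is under a minute more per child interview, small edits to the guide and a sentence or two in Section 4.
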